3.0 Objectives

Our **Specific Aims** include:

Aim 1. Refine and pilot the Continuing the Conversation (CTC) intervention.

- **1a.** With input from Veteran Advisors, we will refine our CTC intervention, adapting content from our previously developed online videos (stories told by African-American Veterans who have controlled their hypertension) to create narrative-aligned text messages ('storyteller texts').
- **1b.** We will pilot the process of providing guidance to 20 Veterans as they (a) **View** Veteran videos; (b) **Select** a preferred video narrative; (c) Sign up to **Get** texts through HealtheDialog Texting system.

Aim 2. Test CTC by conducting a randomized controlled trial with the following characteristics:

- **Setting and Sample:** 600 African-American Veterans with hypertension. Veterans will be recruited from two VA healthcare sites with known disparities in hypertension control.
- **Design:** Veteran-level randomization, stratified by site and within-site stratification by gender
- **CTC Intervention:** An integrated peer narrative-based intervention (VIEW > SELECT > GET), beginning with VIEWing of VA Stories narratives, followed by SELECT a favorite Veteran Storyteller, and then GET favorite Storyteller "narrative-aligned" text messages over 6 months
- **Control:** 6-month HTN management assessment text messages without narrative component

Aim 3. Evaluate CTC effectiveness, and mediating factors, and conduct a cost analysis.

- We hypothesize that, for those in the CTC Intervention group as compared to the control:
- **Hypothesis 1:** The difference in blood pressure from baseline to 6 months (primary outcome) will favor CTC intervention group by 5mm Hg, compared with the change in control.
- **Hypothesis 2:** Self-efficacy and hypertension management behaviors during 6-month follow-up will be greater for those in the CTC intervention group than comparison.
- We hypothesize that **(H3)** the effect of CTC on blood pressure will be mediated by the proximal measures of **(H3a)** cognitive and emotional processes (i.e.: emotional engagement with stories, self-efficacy) and **(H3b)** hypertension self-management behaviors. We will further measure the marginal cost of this intervention.

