Videos, Procedures surrounding Video viewing and Selection of text protocol: Our team has already created and tested video-recordings available online (Appendix 1) in which African-American Veterans with controlled HTN share their stories (describing challenges and successes managing their HTN).

- Procedure for Intervention group participants.

VIEW videos: During the over the phone visit, the Research Assistant (RA) will ensure the participant has a quiet space and online access to the 5 Veteran narratives so that participants can view the 5 brief videos. We will send the link to the videos to the participant if they have given permission to contact via email, otherwise we will send them the link via text, or read it aloud to them. Veterans will not be provided DVDs but since they will be provided with the web address they can access the videos on their own if they wish to re-view videos. If the Veteran requests use of a virtual platform to watch the videos, such as WebEx, Zoom, or other approved platform, the RA will create a session and utilize the shared screen to watch the videos only. No PHI or PII will be shared during this time.

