SELECT a Preferred Veteran Storyteller: After the Veteran has viewed the videos, the Veteran will complete the final brief section of the survey. If necessary the RA will re-contact via phone or by text at that time to ask survey questions. The RA will remind participant of the five storytellers they just watched. If at that time the Veterans wish to pause and go back to see any videos they missed or re-view any videos, they may. The RA will explain that this selection will inform the content of the text messages sent to the Veteran over the upcoming 6 months, with the goal of providing text messages that work well for the Veteran. The RA will explain that some messages will include either (a) direct quotes from this storyteller, referencing back to or building further upon the video-recorded story; or (b) references to topics related to those which the Veteran talked about. **If participant is not reached following watching the storyteller videos, the site coordinators will initiate a text requesting that they select a storyteller. If they do not reply to the text request and are still unreachable 2-weeks after the baseline visit occurs, we will select a storyteller for them by selecting, in order, from a list of the 5 storytellers; when all 5 have been assigned in this way, we will start back at the top of the list. Lists will be maintained separately at the two sites. Participants will be told during the baseline visit, once assigned to intervention, after watching the videos that if they do not select a storyteller for some reason, they will be assigned one by the research team.**

GET preference-based, narrative-aligned CTC texts: Veteran participants will receive text messages, with messages chosen to align with their selected storyteller. These texts will be delivered using the VA HealtheDialog texting system, described above. In the baseline phone visit, Veterans will receive an orientation to the texting system, over the phone. RAs will enroll Veterans in HealtheDialog and provide education on use of the system and what to expect from the CTC protocol.

- Procedure for Control Group Participants:

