Veterans will have an over-the-phone visit during which the RA enrolls each Veteran in the control texting protocol and collects baseline data including blood pressure and all Baseline elements described in Section 5.5. Veterans will then receive 6 months of text messages, receiving one assessment text weekly with a follow-up reminder if needed, and they will also receive responses to their reply to assessment texts.

CTC Texting Protocol (content and tasks required from participant):

- Narrative-aligned Texts (“Storyteller Texts”): Participants will be invited to choose the Veteran storyteller whom they found most compelling; this choice will then be used to guide selection of a longitudinal texting protocol designed to ‘continue the conversation’ over a six-month period. Storyteller texts are intended as cues, triggering recollection of the foundation laid through the initial story viewing. Our intention is to use these texts to engage participants on both an emotional and cognitive level. We will adapt transcribed content from our VA Stories videos to create narrative-aligned texts (“storyteller texts”) (Appendix 3). Adaptation of transcribed content will be conducted with 3 goals: to identify quotations for which (1) the clarity and length are conducive to incorporation into a stand-alone text message, (2) content maps to our conceptual model and (3) to ensure that quotations convey the storyteller’s ‘voice’ (their own words/phrases). Where direct quotations conducive to incorporation into text are not available, narrative-aligned texts will convey messages that reference and build upon the story content.
- Our team has already completed qualitative analyses of full (unedited) video recordings of Veteran narrators. Completed analyses identified story segments guided by storytelling best practices and informed by constructs from our conceptual model; this work will inform our selection of content for storyteller texts.

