Hypothesis 1: (Primary Hypothesis) The difference in blood pressure from baseline to 6 months will favor CTC intervention group by 5mm Hg, compared with the change in control.

H1 postulates a difference-in-differences between study groups. We will use study group, assessment time, and group-time interactions as predictors in regression models. With this parameterization, the coefficient for the group-time interaction represents differential change for intervention vs. comparison. Multilevel mixed-effects generalized linear models will: (1) model the outcome distribution with an appropriate link function; (2) account for clustering of repeated measures within individual; (3) adjust for observed group imbalances as secondary analyses; and (4) support secondary mediation analyses as described below. The most general structure of the mixed model is $y = X\beta + Z\gamma + \epsilon$, where the y matrix is the observed outcomes, β is a vector of fixed-effect parameters with design matrix X , γ is a vector of random-effect parameters with design matrix Z , and ϵ is a random-error vector. We will assume that γ is independent of ϵ and has a multivariable normal distribution with mean $\mathbf{0}$. We will examine residuals to seek gross violations of underlying assumptions, and explore approaches to address violations such as variable transformation, outlier trimming, or placing bounds on the extent that extreme observations can affect conclusions.

Hypothesis 2: Self-efficacy and hypertension management behaviors during 6-month follow-up will be greater for those in the CTC intervention group than comparison.

As Self-efficacy and HTN management behaviors (salt intake, physical activity, doctor-patient interaction, monitor BP) will be measured as self-report at baseline and follow-up, we can measure these as differences in change ("difference-in difference") between study groups, and mirror the analysis plan for H1.

In addition to self-report, for "Take your medicines" (medication adherence) we will use administrative data to calculate refill-based measures (ie: MPR) for each HTN medication and average these over six-month periods (before and during intervention). We will again use a repeated measures analysis (like H1).

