Secondary Analyses: Covariates to account for substantial imbalances in group characteristics will be added to our main regression models. Secondary analysis will occur for the separate measures of HTN management behaviors and BP change. As in our prior trials, we will also conduct secondary stratified analyses above and below the median mean arterial pressure at baseline (in our prior VA stories, we found the effect greater in those below the median baseline BP (see Section B5.b)). We will also analyze effect by site, by chosen storyteller and by age group. Further, using the administrative data for MPR, we have a pragmatic opportunity to study sustainment of effect after the six-month CTC is completed. For the subset of patients with six-months completed before Year 4, we will also calculate MPR six months after the end of CTC. In a secondary model, three time periods (before, during, after CTC) will be jointly tested using "segmented regression" to account for the three time periods.

Hypothesis 3: The effect of CTC on BP will be mediated by the more proximal measures of (H3a) cognitive and emotional processes (i.e.: emotional engagement with stories, self-efficacy), and (H3b) HTN management behaviors.

For this hypothesis, we will conduct a formal mediation analysis. Initial methods will follow Barron and Kenny's

protocols, with more recent advances developed by MacKinnon. Mediation occurs when an intervention changes the rate of uptake of an intermediate process that directly influences outcome. Mediation analysis can help to disentangle the mechanisms which may contribute to intervention effectiveness. We will estimate the proportion of the intervention effect that is transmitted through each of these mediators and quantify the precision of these estimates with 95% bias-corrected and accelerated bootstrap confidence intervals. Thus, we will be able to quantify the relative proportional mediation for each of the measures listed in Hypothesis 2.

Power Calculations

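### The SAP analyses the CTC effect by chosen storyteller, but that choice is made after randomisation and only in the CTC arm, so no randomised comparison per storyteller exists

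*SAP*

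**What the plan says.** The SAP, Analysis Plan, Secondary Analyses, puts three factors in one sentence: "We will also analyze effect by site, by chosen storyteller and by age group". It names no comparator, model or assumptions for the storyteller item. Under Hypothesis 1 the SAP defines what an effect is in its models: "the coefficient for the group-time interaction represents differential change for intervention vs. comparison".

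The Protocol describes the two arms as follows.

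- **CTC arm (5.1, VIEW and SELECT).** The research assistant arranges "online access to the 5 Veteran narratives so that participants can view the 5 brief videos", and the Veteran then picks one storyteller. The order of events is clear from the notice that Veterans receive at baseline: "once assigned to intervention, after watching the videos that if they do not select a storyteller for some reason, they will be assigned one".
- **CTC Veterans who make no choice (5.1, SELECT).** If a Veteran does not answer the text request and is still unreachable two weeks after baseline, "we will select a storyteller for them by selecting, in order, from a list of the 5 storytellers". Each site keeps its own list.
- **Control arm (3.0 and 5.1).** Controls get "6-month HTN management assessment text messages without narrative component". Their procedure reads: "Veterans will have an over-the-phone visit during which the RA enrolls each Veteran in the control texting protocol and collects baseline data". After that come six months of texts, "receiving one assessment text weekly with a follow-up reminder if needed".

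Table 8, in both documents, has one survey item for the selected video. It is collected only at the time point just after viewing. No item records a control Veteran's preference, and no item separates a chosen storyteller from an assigned one.

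**The concern.** A treatment effect within a subgroup needs the same subgroup in both arms. Site and age group meet that condition because they are fixed before randomisation. Storyteller choice does not: nobody knows which controls would have chosen storyteller A, so the Veterans who chose A have no matching controls.

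Veterans drawn to different storytellers may differ in age, sex, baseline blood pressure or motivation. Any of these can move the six-month change in blood pressure without one story working better than another. Because the item stands beside two valid subgroup factors and uses the word effect, its result could be reported as a set of storyteller-specific CTC effects, which randomisation does not support.

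The list rule adds a smaller question. Some CTC Veterans may carry a storyteller label without having chosen, and the SAP does not say how the analysis treats them.

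**Working it through.** **1. Is the factor defined in both arms before randomisation?**

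| Factor | Fixed before randomisation | Known in control arm |
|---|---|---|
| Site | Yes (stratification factor) | Yes |
| Age group | Yes | Yes |
| Chosen storyteller | No, follows assignment to CTC | No, not collected |

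Only the third fails, and it fails on both counts.

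**2. Inputs for precision.** From the SAP, Power Calculations: 600 Veterans, 85% follow-up, SD 18 mm Hg, within-person correlation 0.5, target 5 mm Hg, two-sided alpha 0.05. From the Protocol: five storytellers. Assumed, because not stated: 1:1 allocation and an even spread over storytellers.

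**3. The SAP's own figure.** SD of change = 18 × √(2 × (1 − 0.5)) = 18. Followed up per arm = 300 × 0.85 = 255. SE = 18 × √(2/255) = 1.59. Power = Φ(5/1.59 − 1.96) = 0.88. At 82% follow-up (246 per arm) it is 0.87. The claim of over 80% power is reproduced.

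**4. One storyteller against all controls.** Followed up per storyteller = 255/5 = 51.

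- SE = 18 × √(1/51 + 1/255) = 2.76 mm Hg.
- Power for 5 mm Hg = Φ(5/2.76 − 1.96) = 0.44.
- Difference detectable with 80% power = (1.96 + 0.84) × 2.76 = 7.7 mm Hg.

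For assumed shares of 10% to 50% of the CTC arm, power runs from 0.27 to 0.73.

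**5. Spread expected by chance.** Suppose all five storytellers work equally well. Each mean change has SE 18/√51 = 2.52. The range of five independent normal means was simulated.

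| Assumption | Mean best-to-worst gap | Probability gap exceeds 5 mm Hg |
|---|---|---|
| Even choice, SD 18 | 5.9 mm Hg | 0.63 |
| Even choice, baseline-adjusted SD 18 × √(1 − 0.25) = 15.6 | 5.1 mm Hg | 0.48 |
| Uneven choice (35/25/20/12/8%), SD 18 | 6.7 mm Hg | 0.71 |

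These figures measure sampling noise, not self-selection.

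**6. How self-selection would act (all inputs assumed).** Let every storyteller have the same true effect of −5 mm Hg. Let an unmeasured factor explain 10% of the variance in change. Let it move preference towards one storyteller and away from another by 0.2 or 0.4 log-odds per SD. Simulated apparent effects against all controls then run from −3.8 to −6.2 (0.2) or from −2.8 to −7.1 mm Hg (0.4). With no link to preference, all are about −5. This shows the mechanism; it does not estimate the bias in this trial.

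**7. List-assigned Veterans (rate assumed).** If 10% of 300 are assigned by rotation, that is 30, or 6 per storyteller, and 270 choose.

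- Storyteller picked by 20% of choosers: 6/(54 + 6) = 10% assigned.
- Storyteller picked by 5% of choosers: 6/(13.5 + 6) = 31% assigned.

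At a 20% rate the shares are 20% and 50%.

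**The case against.** The strongest reply is that this is one clause among the secondary analyses, with no hypothesis, power claim or decision rule attached, and that a description within the CTC arm fits the same words. It is right about scope. On wording it is less convincing: the sentence says effect, the SAP defines effect as CTC against control, and storyteller is listed like two true baseline factors.

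Several stronger readings are tempting and should not be drawn.

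- **The 5.9 mm Hg gap shows the bias.** It does not. A randomised five-level subgroup of this size would vary as much, and so would the descriptive analysis recommended here. It is also the largest of several differences, so it is not the same kind of quantity as the 5 mm Hg two-arm target.
- **The SAP pools non-choosers with choosers.** It does not say so. It speaks of the chosen storyteller, the Table 8 item is asked just after viewing, and the sites keep assignment lists. Mixing is possible, because neither document separates the two groups for analysis. Nor do the documents show that list-assigned Veterans are less engaged.
- **The result would decide which stories are kept.** Protocol 2.0 plans video links and selection cards if the trial succeeds. It does not say that stories will be ranked or dropped on this analysis.
- **No storyteller-specific effect could ever be estimated.** That is too absolute. Principal stratification, with choice predicted from baseline covariates, is one route, but it needs strong assumptions and the SAP states none.

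The documents also never say outright that controls see no videos; this follows from the arm descriptions. The videos are online, so chance viewing is not excluded, but a control choice would still not be recorded.

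**Conclusion.** The concern holds. As worded, the SAP calls for an effect by a factor that arises after randomisation and only in the CTC arm. The available contrasts are not randomised and are open to self-selection bias whose size the documents do not allow anyone to state. A larger sample would improve precision but would not remove that bias.

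The precision figures depend on 1:1 allocation, even choice and the SAP's SD, correlation and follow-up; uneven choice makes them worse for the less popular storytellers.

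A reader might infer that the trial's main result is in doubt. It is not: the intention-to-treat comparison under Hypothesis 1 and its power do not use storyteller choice. The analyses by site and by age group do not share this defect. The plan should be changed, but the change is limited to one secondary analysis.

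**What to change.** 1. In the SAP, Secondary Analyses, remove chosen storyteller from the factors by which the effect is analysed, leaving site and age group.
2. Add a separate item: BP change by storyteller within the CTC arm, labelled descriptive and non-randomised, adjusted for baseline BP, age, sex and site, with one overall test across the five and no treatment-effect wording. Report confidence intervals, so that the low precision is visible.
3. Add a field to the data set recording whether the storyteller was chosen or assigned from the list, and show list-assigned Veterans separately.
4. If a CTC-against-control effect per storyteller is still wanted, pre-specify the method and its assumptions before outcome data are examined.

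The cost is a short SAP edit and one yes/no field, which the site assignment lists should help to fill. The small downside is that no storyteller-specific CTC effect is claimed unless step 4 is taken.

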17-185 *“Continuing the Conversation: A Multi-site RCT Using Narrative Communication to Support Hypertension Self-Management among African-American Veterans”*

Funding Agency: HSR&D

Principal Investigator/Study Chair: [name] MPH

February 10, 2022 / Version 7

Abstract

Background: Compared to other racial and ethnic groups, non-Hispanic African Americans have an earlier onset and higher prevalence of hypertension (HTN) as well as a disproportionately higher risk of complications, leading to higher rates of cardiovascular morbidity and mortality. In previous work, we used storytelling in African Americans outside the VA, yielding significant improvements in blood pressure. We translated these findings to the VA, developing and testing video-recorded Veteran narratives which we showed to African-American Veterans. We demonstrated significant differences in intention to change HTN management behavior immediately after video viewing; however, effects on blood pressure were not sustained, and six-month outcomes revealed only modest benefit over control ($p = 0.06$). Our findings highlight the need for longitudinal support to sustain the storytelling effect. Our proposed study provides longitudinal support via text messages, incorporating content from the participant's chosen peer narrative as a means of sustaining motivation and engagement in HTN self-management.

Innovativeness: Our study, "Continuing the Conversation," is a novel integration of peer narrative communication into technology. While use of an informatics tools (texting) as a channel to support self-management is not novel per se, the extension of a narrative via longitudinal texting is an innovative mechanism for supporting and sustaining HTN self-management behaviors. Our **Specific aims include:**

Aim 1. Refine and Pilot the Continuing the Conversation (CTC) intervention. Previously, we created video-recorded stories told by African-American Veterans with HTN, describing their self-management strategies. We will refine CTC by adapting content from these videos to create narrative-aligned texts and we will pilot CTC with 20 Veterans.

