We will pilot the process of providing in-person guidance to 20 Veterans as they (a) View the Veteran videos; (b) Select a preferred video narrative; and (c) Sign up to Get texts through the HealtheDialog Texting system. The pilot will contain usability testing and a formative evaluation of the Veterans' experiences. We will purposefully sample 10 Veterans from each site (total of 20) and will aim to include 4 women Veterans (2 per site). We will pilot the process of (1) guiding the Veteran in selection of a preferred veteran storyteller after viewing all stories; (2) using this choice to inform selection of a texting protocol; (3) Receipt of 1 month of texts; and 4) follow-up assessment at the end of 1 month. We will assess feasibility of two options for Veterans to access texts: (a) via regular texting, available on all text-enabled phones; (b) via HealtheDialog 'App' which allows study team tracking of text opening (but is available only on Smart phones). We will assess completion rates (how many Veterans have difficulty or discontinue texts early) and perceptions (e.g. "I felt connected to the storyteller while receiving texts", "the number of texts was: too few, just right, too many"). The formative evaluation will include a qualitative interview with all Veteran participants to understand their experiences with the CTC protocol. Our semi-structured interviews will cover their overall experiences, as well as specific questions about the enrollment process, frequency and content of messages. Interviews will be audio-recorded with brief, descriptive field notes. We will then Test CTC by conducting a randomized controlled trial with the following setting and sample: 600 African-American Veterans with poorly controlled hypertension. Veterans will be recruited from two VA healthcare sites with known disparities in hypertension control.

Data Collection

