Missingness not at random may introduce bias. Advance planning through sound data collection and quality control will be used to minimize this bias. We will use all available data regardless of whether a patient has a complete record. Group means will be reported as least-squares means, the predicted marginal mean values, or those that would be expected with a balanced design. Participants with missing data will be compared to those without. Inverse probability weight in and pattern-mixture modeling using the longitudinal data structure, for non-ignorable missing data, will be considered.

Covariates for Adjustment Models

We will look at the balance of randomization and adjust for demographics and behavioral variables if imbalanced.

Data Transformations

N/A

Analytical Sets

We intend to include all patients in intent to treat analysis.

Monitoring Adverse and Serious Events

Because this is a low-risk trial of an educational DVD, we do not expect SAE's or AE's. We will plan to report any SAE's defined as death of participant or hospitalizations reported at 6-month follow-up.

At the time of recruitment, patients experiencing hypertensive urgency, as defined by JNC as Blood Pressure Systolic \geq 180 OR Diastolic \geq 120, regardless of symptoms, will be referred to urgent care and a notification letter will be sent to their primary care physician. If a patient reports symptoms related to the hypertensive urgency, even if before viewing the intervention DVDs, this will also be reported as an AE. AE's also include stress related to watching the DVD. All AE's reported at baseline and 6-month follow-up will be recorded and submitted at Continuing Review.

Analysis Plan

We will first identify key distributional features for all variables of interest (non-normality, skewness, ceiling or floor effects, presence of implausible values, outliers, etc.) and calculate descriptive statistics. We will document recruitment and retention with a CONSORT diagram. Following best practice, baseline differences between intervention and comparison groups will be based on standardized differences, not simply tests of statistical significance. All primary hypotheses will be tested by intent-to-treat; secondary analyses will account for important covariate imbalances between groups, levels of adherence to the intervention protocol, and missing data. All analyses will be two-sided, with alpha error = 0.05.

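### Subgroup effects by site and unspecified age group are planned at two-sided 0.05 with no interaction test; one interaction term each, with age kept continuous, would be more reliable and more powerful

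*SAP*

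**What the plan says.** The SAP's Analysis Plan sets one error level for everything: "All analyses will be two-sided, with alpha error = 0.05". H1, the difference in blood pressure change between arms, is labelled the primary hypothesis and is tested by a group-by-time interaction.

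The Secondary Analyses paragraph then adds subgroup work on blood pressure. For baseline pressure it says "we will also conduct secondary stratified analyses above and below the median mean arterial pressure at baseline", with the reason that "in our prior VA stories, we found the effect greater in those below the median baseline BP". It continues: "We will also analyze effect by site, by chosen storyteller and by age group".

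Neither document gives age cut points or a number of bands, a treatment-by-subgroup interaction test, a multiplicity adjustment, or a statement of how a subgroup result is to be read. The analyses are called secondary; they are not called exploratory.

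**The concern.** With a p-value threshold for every analysis and no rule for interpretation, the plan allows a single site or age band with p < 0.05 to be reported as the place where CTC works, even when the overall comparison is not significant. A result within one stratum does not show that the effect differs between strata; that needs an interaction test, and none is stated. The number of age bands is open, so the number of chances for a nominal positive is open too.

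There is also a cost in efficiency. Whether the effect changes with age is a sensible question, but cutting age into bands discards information that the trial will already hold. At stake are the reliability and power of the secondary subgroup findings, not the primary conclusion.

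**Working it through.** **Inputs.** Two sites (SAP, Rationale for Study Sample Size); two MAP strata split at the median (Secondary Analyses); two-sided 0.05 (Analysis Plan); 600 recruited, 85% follow-up, correlation 0.5, SD 18, difference 5 mm Hg (Power Calculations). Assumed, because not stated: 1:1 allocation, 2 to 4 age bands, equal strata, factors independent of each other. The storyteller analysis is left out of the count, because only the CTC arm chooses a storyteller and the comparison is of a different kind.

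**The plan's own figure.** SD of change = √(2 × 324 × (1 − 0.5)) = 18. With 255 completers per arm, power for 5 mm Hg is 88.0%; at 82% follow-up (246 per arm) it is 86.9%. The stated power of over 80% is reproduced. In half the sample, power for 5 mm Hg is about 60%. The documents give no subgroup error rate to reproduce.

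**Separate tests in each stratum, no true effect.** Each stratum's z statistic is standard normal, so sample size and SD drop out. Strata of the same factor are independent. Strata of different factors with shares p and q overlap, and their z statistics correlate √(pq), for example 0.5 for two halves. Simulation with 1,000,000 draws, keeping this overlap:

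| Age bands | Site + age: any p < 0.05 | of which any favouring CTC | Site + age + MAP: any p < 0.05 | of which any favouring CTC |
|---|---|---|---|---|
| 2 | 16.1% | 8.2% | 21.1% | 10.7% |
| 3 | 20.3% | 10.4% | 25.0% | 12.8% |
| 4 | 24.4% | 12.6% | 28.8% | 14.9% |

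Sites split 60/40 with uneven age bands leave the three-factor range at 21-29%. Among null trials in which the overall H1 test is not significant, a stratum favouring CTC appears in about 6-11% (site plus age) or 9-13% (with MAP).

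**One interaction test per factor.** Site and age: 1 − 0.95² = 9.8%. Site, age and MAP: 1 − 0.95³ = 14.3%. These do not depend on the number of age bands.

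**Cost of banding age.** Suppose the effect changes linearly with age, age is roughly normal, and a one-degree-of-freedom test on continuous age has 80% power. Its non-centrality is (1.960 + 0.842)² = 7.85. With k equal-sized bands, only the between-band share of the age variance is kept, and the joint test has k − 1 degrees of freedom:

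| Bands | Share kept | Non-centrality | Power |
|---|---|---|---|
| 2 | 0.637 | 5.00 | 61% |
| 3 | 0.793 | 6.23 | 60% |
| 4 | 0.861 | 6.75 | 57% |

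**The case against.** The strongest reply is that the plan already has a hierarchy. H1 is primary, power is calculated only for the three hypotheses, and the subgroup analyses are listed as secondary with no hypothesis attached. The 0.05 is a level per analysis; no familywise rate is promised for secondary results. All of this stands, and it is why the point is minor.

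A reader might go further and infer that a useless CTC will yield a false subgroup claim in 21-29% of trials. The documents do not support that as a flat statement. Only the MAP analysis is described as stratified; for site and age the text says just that the effect will be analysed by them. H1 is itself built on an interaction term, so an interaction analysis is an equally natural reading, and it gives 10-14%. The 21-29% also needs the MAP strata and an assumed number of age bands, and it counts strata that favour control.

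A reader might also infer that the earlier trial missed its main result and was rescued by a subgroup. The Protocol Abstract reports p = 0.06 for six-month outcomes without saying that this was the primary comparison. The SAP's remark about the median split gives no p-value and points to a section that is not in these documents. The inference cannot be drawn.

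Lastly, a look at the effect by site is a routine consistency check in a two-site trial. That is right; the question is how it is tested and read, not whether it is done.

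**Conclusion.** The point holds in a limited form. The secondary subgroup analyses by site and age have no stated test of difference, no age bands and no rule of interpretation, while 0.05 applies to each. Under separate stratum tests and 2 to 4 age bands, a null CTC gives some stratum with p < 0.05 in about 16-24% of trials for site plus age, and 21-29% with MAP; about 8-13% and 11-15% have one that favours CTC. Interaction tests bring the chance of any nominal positive to about 10-14%. Banding age would cut a power of 80% to about 57-61% if the change with age is roughly linear and the bands are tested jointly.

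These figures rest on equal, independent strata; modest imbalance barely moves them. The type I error of H1 is not affected. Severity: minor.

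**What to change.** In the SAP's Secondary Analyses paragraph:

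1. Replace the analysis by age group with one arm-by-time-by-age term using continuous age. Age bands may be used for display only.
2. Assess site by one arm-by-time-by-site term.
3. State that subgroup effects on blood pressure are exploratory, reported as estimates with 95% confidence intervals and without significance claims within strata, whatever the result of H1.

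This takes two or three sentences and no new data, since age and site are already collected. The cost is a linearity check for age, and giving up stand-alone subgroup claims at p < 0.05.
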